7.1.1. Clinical efficacy data (collected at each clinical site)

Clinical efficacy (clinical site)

- Occurrence of *P. aeruginosa* pneumonia (primary variable)
The diagnosis of pneumonia will be assessed under blinded conditions by an independent panel of experts prior to stopping the study
- Occurrence of death (excluded if death within 3 days and not elicited by *P. aeruginosa*)
- Time to pneumonia, to exitus (Day -1), or to bacteremia
- Time to extubation (Day n-1)
- Overall outcome (until Day n+7)
- Duration of hospital and ICU stay
- Cost assessment
- PaO₂/ FI_{O2}
- Occurrence of infections to other bacterial strains

7.1.2. Pharmacodynamic data performed in local laboratory

A. Tracheal aspirates (on Aspirate 1)

- Collection daily
- Quantitative culture for *P. aeruginosa* (CFU/mL) on Day -1, 1, 3, 6, 9, 12, 15, 18 and last day (Day x, or Day n-1, or Day 20)
- Isolate *P. aeruginosa* strain daily and store at -70°C on skim milk and glycerol
- Emergence of resistance (MIC to *P. aeruginosa* in tracheal aspirate for 11 standard antipseudomonal antibiotics on Day -1 and on last day (Day x, or Day n-1, or Day 20) see list under Section 6.2)
- CFU for other strains from tracheal aspirates if indicated

B. BAL on Day x (or protected brush specimen (PBS) or bronchotracheal aspirate)

- Only for patients with suspected pneumonia for diagnosis
- CFU/mL
- Cellularity

7.1.3 Pharmacodynamic data performed in Geneva laboratory

A. Tracheal aspirates (*ex vivo*, on Aspirate 2)

- Collection daily at study site, storage at -70°C prior to transfer to Geneva
 - Day -1, 1, 3, 6, 9, ..., last day (Day x, or Day n-1, or Day 20) for all patients
 - Daily for pneumonia (n=10) and control patients (n=20)
 - Daily for patients on antibiotherapy
- Parameters
 - Content for autoinducer homoserine lactones: 3-oxo-C₁₂-HSL and C₄-HSL **and/or**
 - mRNA for LasB elastase (lasI, rhlI)

B. Respiration device on Day n

- CFU/cm²
- Autoinducer content

C. Isolated *P.aeruginosa* strains from tracheal aspirate 1 and respiration device (*in vitro*)

- Day -1, 1, 3, 6, 9, ..., last day (Day x, or Day n-1, or Day 20) for all patients Daily for pneumonia (n=10) and control patients (n=20) selected on a site basis
- Daily for patients on antibiotherapy
- *In vitro* virulence factor production (elastase, protease, rhamnolipids, cytotoxicity)
- *In vitro* autoinducer production (3-oxo-C₁₂-HSL and C₄-HSL)
- Azithromycin gradient plates for detection of rhamnolipid production (Day -1, or Day x, or Day n-1) to detect possible resistance mechanisms

7.1.4. Safety data

- Adverse event profile (reported by subject, observed by investigator)
- Local tolerance (infusion site if peripheral site)
- Standard laboratory tests (see Appendix B)
- Blood gases
- Vital signs (blood pressure, heart rate, body temperature)
- 12-lead electrocardiogramme (ECG)
- Emergence of non *Pseudomonas* infections

7.2 Description of Study Days

7.2.1 General Recommendations and Procedures for Study

Test drug solutions (Azithromycin or placebo saline as required) will be prepared by the site pharmacist (see Section 5.3, 5.4 and Appendix C) in adequately labeled pouches transmitted to the investigator for storage at 5 °C or 41 °F until 1 hour prior to use. The temperature of the solution must be close to room temperature when infused. The same peristaltic pump should be used throughout the study. The exact

time of start and completion of the infusion will be recorded in the CRF, along with the volume infused (250 mL) and the label. It is not planned to collect retain samples pre or post infusion in this study. Efforts will be made to rotate infusion sites if a peripheral vein is used every 4th or 5th day, or more often in case of local signs. Preference will be given to a central line if available to ensure high blood flow.

Time (T=0) is always calculated from start of test drug infusion. Cannulae will be maintained patent with a slow saline infusion. No other drug may be infused concomitantly using the same i.v. line. A 24 hour time frame between daily infusions should be attempted.

Clearly a **hierarchy** for activities must be followed, collecting predrug (0 hr) samples (tracheal aspirate 1, blood safety, blood for WBC, blood gases, and blood culture if required etc.) or predrug information (vital signs i.e. blood pressure and heart rate, oxygenation, systemic and local tolerance, fever), all before initiating the test drug infusion. The precise time for starting and stopping the test drug infusion, for collecting tracheal aspirate 1 (predrug), aspirate 2 (~6 hours post infusion start), should be recorded in the CRF. ECG will be recorded 1 to 4 hours post infusion start as indicated in the appropriate study schedule and following recommendations of Appendix J. Fever will be measured in late afternoon (around 17:00 o'clock) and vital signs 6 hour post test drug infusion start (around 15:00 o'clock). Systemic and local tolerance will be observed throughout the study, until a week after cessation of therapy for adverse events for the former (i.e. Day n+7).

7.2.2 Prestudy Screening (Day -1)

The following examinations and tests may be carried out over 2 or occasionally 3 days as required for obtaining results or confirmation for each subject before entering the study:

- Check likely adequacy of inclusion/exclusion criteria
- Explain study to the patient (or to a close family member if not conscious or not in a position to make a decision) and obtain written approved consent
- Confirm inclusion/exclusion criteria with strong emphasis on inclusion criteria (assisted ventilation anticipated to last for at least 3 more days, colonization of tracheal aspirate by *P. aeruginosa*, APACHE II score between 15 and 25, etc.)
- Assign a screening subject number
- **Record:**
 - Complete physical examination and medical history, including age, sex, and race
 - Height and weight (from patient dossier)
 - Blood pressure, heart rate, respiration rate (8:00, 14:00)
 - Body temperature (tympanic or oral) 7:00 (and 17:00 if selected)
 - Blood (see Appendix B)
 - Hematological profile
 - Blood chemistry
 - WBC & CRP
 - Urinalysis screening (see Appendix B)
 - 12-lead electrocardiogramme
 - Blood gases
 - Oxygenation: Pa_{O2}/ FI_{O2}
 - Lung X-Ray

- Apache II score
- CPIS
- Tracheal aspirate 1 (~8:00) for transfer to local laboratory (for parameters see Section 7.1.2)
 - Quantification of *P. aeruginosa* (CFU/mL)
 - Isolation of *P. aeruginosa* strain (storage -70°C)
 - Special Day n-1 assessment for MIC on *P. aeruginosa* strain with 11 antipseudomonal antibiotics (listed under Section 6.2)
- Aspirate 2 (~14:00) for storage at -70°C
- Clinical endpoints

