4.2 Inclusion Criteria

Subjects meeting all of the following criteria will be considered for admission to the study:

- Male and non pregnant female aged 18 to 75 years
- Patients hospitalized in ICU, under mechanically assisted ventilation expected to be mandatory for 3 days or more
- Reasonable survival chance within next few days with an Apache score 10-25 as per Appendix H [Knaus et al 1985]
- Tracheal aspirate found positive to *P. aeruginosa*
- The subject (or a close family member in case of incompetence) understands the procedures, agrees to participate, and is willing to give his written informed consent

Informed consent must be obtained for all subjects before enrollment in the study, by patient or by close family member.

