4.3 Exclusion Criteria

Subjects presenting with any of the following will not be included in the study:

- Poor prognosis as judged by Apache II score >25
- Pregnant females
- Grossly under- or overweight (BMI <18 or >29)
- Ongoing therapy with a macrolide (clarithromycin, erythromycin, azithromycin, telithromycin)
- Known allergy to any macrolides
- Proven *P. aeruginosa* pneumonia (with documented CFU>10⁴ in BAL or PBS)
- Ongoing antipseudomonal therapy with a susceptible colonizing strain as proven by antibiogramme*

* A list of recommended antibiotics deprived of antipseudomonal activity is provided in Section 6.2 to facilitate the choice of the investigators and to homogenize antibiotic treatment according to type of infections. For patients on antibiotherapy with activity against pseudomonas prior to study entry, they will be maintained in the screening phase for 48 hrs, pending results of antibiogramme on the colonized strain. If found to be susceptible to the antibiotic used, the patient will be excluded from the study; if found to be resistant, the patient will be included in the study (also see Section 6.2)

- Anticipated short duration of mechanical ventilation (≤ 3 days)
- Known drug interaction which could interfere enough with absorption, metabolism, or excretion and thus could decrease efficacy or raise safety concern despite plasma drug monitoring of concomitant therapy (for examples see Section 6.2)
- Severe hepatic insufficiency (type C i.e. score >10 on Child Pugh scale, Appendix A) [Pugh et al 1973]
- Sick sinus syndrome or known long QT syndrome or $QTc >500$ msec
- Recent donation of blood or participation in another clinical trial within 3 months (Europe) or 1 month (USA)
- Any situation exposing the patient to higher risk or possibly confounding results of the study

Any local or country specific regulations must be respected. Any waiver of the inclusion and exclusion criteria listed above must be approved by the investigator and by the monitor on a case-by-case basis prior to enrolling the subject. This must be documented by both the monitor and the investigator.

No subject will be allowed to enroll in this study more than once if study drug was administered. However a patient may be screened on a 2nd occasion under another screening number if he did not meet all inclusion and exclusion criteria in the first instance.

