Serum creatinine (µmol/L)	 ≥3.1	 1.8-3.0	 1.3-1.7		 0.5-1.2		 <0.5		
Acute renal failure: double score									
Hematocrit (%)	 ≥60		 50-59.9	 46-49.9	 30-45.9		 20-29.9		 <20
WBC (ths/mm ³)	 ≥40		 20-39.9	 15-19.9	 3-14.9		 1-2.9		 <1
Glasgow Coma Score (GCS) Score = 15 minus actual GCS									
A Acute Physiology Score (APS): Sum of 12 variables									
Serum HCO ₃ (venous mmol/L) Not preferred, only if no arterial pH	 ≥52	 41-51.9		 32-40.9	 22-31.9		 18-21.9	 15-17.9	 <15

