*** Definitions**

Liver: Biopsy proven cirrhosis and documented portal hypertension; episodes of upper GI bleeding attributed to portal hypertension; prior episodes of hepatic failure/encephalopathy/coma

Cardiovascular: New York Heart Association Class IV

Respiratory: Chronic restrictive, obstructive or vascular disease resulting in severe exercise restriction; documented chronic hypoxia, hypercapnia, secondary polycythemia, severe pulmonary hypertension (>40 mm Hg) or respiratory dependency

Renal: Receiving chronic dialysis

Immuno-compromised: Drug-induced by recent and high dose steroid, chemotherapy, radiation, cyclosporine...
Disease-induced in leukemia, lymphoma, or AIDS

APACHE II		Score
APS Points	A	
Age Points	B	
Chronic Health Points	C	
Total APACHE II Score		
		Maximum possible score : 71
		Maximum clinical score: 55
		Range for selection: 10 to 25

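### The entry criteria contradict themselves: two APACHE II windows, a creatinine row whose printed unit cannot be right, and two definitions of Child-Pugh C

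*Protocol*

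**What the plan says.** **APACHE II window.** The inclusion criterion in Section 4.2 asks for a patient "with an Apache score 10-25 as per Appendix H". The score summary at the end of Appendix H agrees: "Range for selection: 10 to 25". Section 7.2.2, where the site confirms eligibility and is told to pay particular attention to the inclusion criteria, requires an "APACHE II score between 15 and 25". Section 4.3 sets only the upper end: "Poor prognosis as judged by Apache II score >25".

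**Creatinine row.** The row in Appendix H is labelled "Serum creatinine (µmol/L" (closing bracket omitted here). Its bands are ≥3.1 (+4), 1.8–3.0 (+3), 1.3–1.7 (+2), 0.5–1.2 (0) and <0.5 (+2), and the points are doubled in acute renal failure.

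**Child-Pugh.** Section 4.3 excludes severe hepatic insufficiency, given as "type C i.e. score >10 on Child Pugh scale, Appendix A". Appendix A, which that line cites, sets grade A at 5 to 6, grade B at 7 to 9 and grade C at 10 to 15.

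**The concern.** APACHE II is a core entry criterion. If two sites read different pages, one could enrol a patient scoring 12 and the other could turn the same patient away. The page used also decides whether that patient needs the documented waiver described in Section 4.3.

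The creatinine label matters because Section 4.2 requires scoring by Appendix H, and Section 7.3 leaves clinical chemistry to each site's own laboratory in a multinational trial. A site with µmol/L results has a table that appears to be in its own unit but cannot be used as printed. A site with mg/dL results would score as the bands seem to intend. The two would then apply different effective entry limits, and the scores recorded on Day -1 (Section 7.2.2) and Day n-1 (Section 7.2.5) would not be comparable across sites.

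The Child-Pugh wording raises the same kind of problem for a single score.

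**Working it through.** **1. The scoring tables, apart from the unit.** Appendix H gives a maximum possible score of 71. Ten variables at 4 points each give 40. Creatinine at 4, doubled, gives 8. The coma item gives 15 − 3 = 12 (taking 3 as the lowest Glasgow score). The physiology score is 40 + 8 + 12 = 60. Adding 6 for age and 5 for chronic health gives 71, which reproduces the stated figure; without the doubling it would be 67. So the point structure is sound and the fault lies in the unit. In Appendix A, five signs scored 1 to 3 give a range of 5 to 15, which matches the printed grades when the two prothrombin rows count as one sign.

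**2. APACHE II windows.** The range 10–25 contains 16 integer scores and 15–25 contains 11. The five in dispute are 10, 11, 12, 13 and 14. No score above 25 is in dispute.

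**3. Creatinine.** Two assumptions come from outside the protocol: 1 mg/dL = 88.4 µmol/L, and normal serum creatinine of roughly 40–110 µmol/L. As printed, the zero-point band of 0.5–1.2 µmol/L would be 0.006–0.014 mg/dL, and the +4 cut-off of 3.1 µmol/L would be 3.1 / 88.4 = 0.035 mg/dL. Read as mg/dL, the zero-point band becomes 44–106 µmol/L and the +4 cut-off becomes 3.1 × 88.4 = 274 µmol/L, both plausible. Row scores, with mg/dL rounded to one decimal:

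| Creatinine, µmol/L | mg/dL | Score as printed | Score if bands are mg/dL | Overstatement |
|---|---|---|---|---|
| 20 | 0.2 | +4 | +2 | 2 |
| 40 to 110 | 0.5 to 1.2 | +4 | 0 | 4 |
| 150 | 1.7 | +4 | +2 | 2 |
| 200 | 2.3 | +4 | +3 | 1 |
| 300 | 3.4 | +4 | +4 | 0 |
| 500 | 5.7 | +4 | +4 | 0 |

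In acute renal failure each overstatement doubles, for example to 4 at 150 µmol/L and 2 at 200 µmol/L.

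The bands could instead be meant as hundreds of µmol/L, which puts the +4 cut-off at 3.1 × 100 = 310. The protocol does not settle 274 against 310, and the two readings score some raised values differently. Neither reading rescues the printed unit.

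**4. Effect on the entry limits.** With a 4-point overstatement, a computed 10–25 corresponds to a correctly scored 6–21 (10 − 4 and 25 − 4), and a computed 15–25 to 11–21. Patients whose correct score is 22–25 would be rejected as above 25. Those at 6–9 would be accepted under the first window, and those at 11–14 under the second.

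**5. Child-Pugh.** Comparing >10 with ≥10 over the scores 5 to 15, only a score of exactly 10 is treated differently.

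**The case against.** The governing criterion and the appendix it cites agree on 10–25, and the outlier is a parenthetical recap in the screening list. That points to a slip, but it does not remove the conflict: the recap sits at the step where eligibility is confirmed, and Section 4.3 gives no lower limit to decide between them.

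Several stronger readings are tempting, and the protocol does not support them.

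- A reader might infer that every patient's total is 4 points too high. The +4 is the row score, and it arises only where µmol/L results are scored literally. The error is 4 only when the correct row score is 0. An 8-point error would need acute renal failure alongside a normal creatinine, an implausible pairing.
- A reader might infer that the comparison between arms is biased. Section 5.3 randomises in balanced blocks of 4 with a separate schedule for each centre, so differences in severity between sites do not by themselves unbalance the arms.
- A reader might infer that a planned efficacy analysis is corrupted. Section 11.3 says only that the score may be used, and APACHE II is not among the efficacy variables in Section 7.1.1.
- A reader might take 5 of 16 scores as a share of patients. It counts integers; the protocol gives no APACHE II distribution and no link to pneumonia risk, so any effect on recruitment or event rate cannot be sized.
- A reader might infer that a grade C patient scoring 10 is admitted. Section 4.3 also names type C and cites Appendix A, which would exclude that patient. The text is ambiguous.

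**Conclusion.** The point holds as three internal inconsistencies of unequal weight. The APACHE II conflict covers scores 10 to 14. The creatinine unit is wrong as printed: that conclusion does not depend on the exact conversion, because the +4 cut-off lies more than tenfold below any normal µmol/L value. The size of the resulting error does depend on assumptions: 4 points at normal creatinine, and 2, 1 or 0 as it rises if the bands are mg/dL. It occurs only at sites that score µmol/L results literally. The Child-Pugh conflict touches one score and is minor.

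The consequence is for who is enrolled and for the comparability of severity scores across sites. Balance between the arms, the significance level and the planned sample size do not depend on it. The first two items need correction before sites open, because enrolment decisions made on a wrong score cannot be undone.

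**What to change.** - State one APACHE II window in Section 4.2, Section 7.2.2 and Appendix H. The upper limit in Section 4.3 already agrees.
- Confirm the creatinine unit and bands against the score that Appendix H reproduces. Print them in one stated unit, with bands that cover every value without gaps, and build the CRF score sheet from them. Multiplying the one-decimal bands by 100 is not enough, since it would leave 121–129, 171–179 and 301–309 µmol/L without a score.
- Make the Child-Pugh wording in Section 4.3 and the grades in Appendix A agree on a score of 10.

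The choice of clinical cut-offs belongs to the sponsor. The cost is a few text corrections and the CRF score sheet, with no additional data collection.

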7.2.3 Study days

Day 1

On the morning of Day 1, prior to infusion of test drug, the following procedures will be performed:

- Adverse events
- Body temperature (tympanic or rectal) ~7:00
- Blood pressure, heart rate, respiration rate (~8:00)
- Blood (see Appendix B)
 - Hematological profile
 - Blood chemistry
 - WBC & CRP
- Specimen for blood culture (only if clinically indicated)
- Blood gases
- Oxygenation: $\text{Pa}_{\text{O}_2} / \text{FI}_{\text{O}_2}$
- CPIS (use X-ray of same day whenever possible, else of previous day)
- Clinical endpoints
- Tracheal aspirate 1 (transfer to local laboratory, for parameters see Section 7.1.2 above)
 - Quantification of *P. aeruginosa* (CFU/mL)
 - Isolation of *P. aeruginosa* strain (storage -70°C)

After these activities the test drug will be infused over 1 hour, usually from 8 to 9 o'clock.

Post treatment activities will include:

- ECG, 1 to 4 hours post infusion start
- Tracheal aspirate 2 (for freezing and transfer to Geneva laboratory for investigation, for parameters see Section 7.1.2 above), collected ~6 hours post infusion start
- Blood pressure, heart rate, respiration rate (~6 hours post infusion start)
- BAL if required medically (suspicion of pneumonia)

- Lung X-ray if required medically or if pneumonia (after Day x)
- Body temperature (tympanic or rectal) ~17:00
- Local tolerance (24 hours)
- Systemic tolerance (24 hours)

Day 2

On the morning of Day 2, prior to infusion of test drug, the following procedures will be performed:

- Systemic adverse events from previous night
- Local tolerance
- Body temperature (tympanic or rectal) ~7:00
- Blood pressure, heart rate, respiration rate (~8:00)
- Blood for WBC & CRP
- Specimen for blood culture (only if clinically indicated)
- Blood gases
- Oxygenation: Pa_{O2}/ FI_{O2}
- Clinical endpoints
- Tracheal aspirate 1 (transfer to local laboratory, for parameters see Section 7.1.2 above)
 - Isolation of *P. aeruginosa* strain (storage -70°C)

After these activities the test drug will be infused over 1 hour, usually from 8 to 9 o'clock.

Post treatment activities will include:

- Tracheal aspirate 2 (for freezing and transfer to Geneva laboratory for investigation, for parameters see Section 7.1.2 above), collected ~6 hours post infusion start
- Blood pressure, heart rate, respiration rate (~6 hours post infusion start)
- BAL if required medically (suspicion of pneumonia)
- Lung X-ray if required medically or if pneumonia (Day x)
- Body temperature (tympanic or rectal) ~17:00
- Local tolerance (24 hours)
- Systemic tolerance (24 hours)

Day 3

On the morning of Day 3, prior to infusion of test drug, the following procedures will be performed:

- Adverse events from previous night
- Local tolerance
- Body temperature (tympanic or rectal) ~7:00
- Blood pressure, heart rate, respiration rate (~8:00)

- Blood (see Appendix B)
 - Hematological profile
 - Blood chemistry
 - WBC, CRP
- Specimen for blood culture (only if clinically indicated)
- Blood gases
- Oxygenation: PaO₂/ FI_{O2}
- CPIS (use results of lung X-ray of same day whenever possible)
- Clinical endpoints
- Tracheal aspirate 1 (transfer to local laboratory, for parameters see Section 7.1.2 above)
 - Quantification of *P. aeruginosa* (CFU/mL)
 - Isolation of *P. aeruginosa* strain (storage -70°C)

After these activities, the test drug will be infused over 1 hour, usually from 8 to 9 o'clock.

Post treatment activities will include:

- ECG, 1 to 4 hours post infusion start
- Tracheal aspirate 2 (for freezing and transfer to Geneva laboratory for investigation), collected ~6 hours post infusion start
- Blood pressure, heart rate, respiration rate (~6 hours post infusion start)
- BAL if required medically
- Lung X-ray whenever possible during the day
- Body temperature (tympanic or rectal) ~17:00
- Local tolerance (24 hours)
- Systemic tolerance (24 hours)

Subsequent study days in 3 day cycles (Day 4, 5 & 6; Day 7, 8 & 9; Day 10, 11 & 12; etc.)

This same treatment and sampling policy, using a 3-day cycle will be used until Day n which may correspond to Day 21 (24 hours after last treatment day i.e. after 20 days of treatment), or to extubation day because mechanical ventilation is medically not required any longer, or to exitus day (due to underlying disease complication, infection due to any strain type and site with or without sepsis, *P. aeruginosa* infections of non pulmonary location) and finally to Day x when *P. aeruginosa* pneumonia diagnosed.

The procedures to be performed daily or every third day are summarized in the Study Schedule (page 10) and as briefly reviewed below:

Day 4, 5, 7, 8, 10, 11, 13, 14, 16, 17, 19	Correspond to Day 2
Day 6, 9, 12, 15, 18	Correspond to Day 3
Day x (pneumonia, see below)	Corresponds to Day 3 with some additional parameters and study drug is terminated once diagnosis confirmed
Day n-1 or Day 20	Corresponds to Day 3, and is last day of test drug (with some additional parameters)

Day n or Day 21

Discharge from study after laboratory safety and physical examination (follows Day n-1, or Day 20, or Day x whenever possible)

If a patient has to be re-intubated within 24 hours he will remain in the study and treatment with study drug continued with 2nd extubation or until Day 20 of treatment whatever happens first. If a patient has to be tracheotomized during the study, he will remain in the study until Day 20 of treatment.

